### ***Experimental setup***

This research is a 2-arm, parallel, open label, non-blinded randomized controlled trial comprised of four independent but interrelated studies with the same participants. The familiarization phase, enrollment verification, obtaining verbal consent to participate, and gathering screening information will be done via phone interview. After screening participants, the Medical and Demographic Questionnaire will be administered. The participant will be e-mailed a link to complete the following surveys/questionnaires: Medical and Demographic questionnaire, Waterloo Footedness Questionnaire to determine their dominant lower extremity, and The Survey of Phantom Limb Awareness and Control that is a commonly used questionnaire regarding phantom phenomena. The participant can use a smartphone, iPad or computer to answer these surveys/questionnaires. Completion of the surveys/questionnaires at the home will respect COVID-19 restrictions by diminishing time spent with the researcher. If the participant is not able to complete the surveys/questionnaires prior to their first scheduled visit, they will be given the opportunity to do at WinPO prior to the physical function evaluation. At the conclusion of the phone interview, the researcher will randomly assign participants to the control or exercise groups. Participants in both groups will then be scheduled for an in-person baseline visit and an in-person follow up visit at WinPO for data collection. The baseline visit will begin with review of expectations and the participant will sign informed consent. All information gathered at the phone interview will be reviewed for accuracy. If the participant has not answered the questionnaires/surveys prior to their baseline visit, they will be provided an iPad to complete the Medical and Demographic Questionnaire, Waterloo Footedness Questionnaire, and The Survey of Phantom Limb Awareness and Control. The baseline testing session will be entirely the same for participants of both groups. During this session, the researcher will assess participants based on their anthropometric variables (i.e. height, weight, body mass index), the morphology of the residual limb (i.e. length, circumference, and volume),—prostheses embodiment as measured by TAPES-R and PEmbS-LLA, and functional abilities as measured by targeted phantom motor execution and FSST, while recording their muscle activities and plantar foot loads. After completion of the baseline testing, the researcher will contact [name], to get information with respect to what surgical closure technique was performed for the participant.

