Physical function assessments will be done by performing targeted phantom motor executions and four-square step test (FSST). Muscle activity will be recorded for the targeted phantom motor executions while participants are not wearing their prosthesis. However, the assessment of FSST needs participants to wear their prosthesis without EMG recording. The justification for this decision is preventing the risk of injury at the skin-prosthesis interface due to electrodes and wires. Foot plantar load will be assessed during targeted phantom motor executions and FSST. Participants will rest 2 minutes while sitting in a chair after each physical function assessment (4 minutes in total). This time will be used to instruct the participant in the testing protocol. Additional time will be provided if requested by the participant. After baseline testing is complete, EMG electrodes and sensors for the foot plantar load will be removed. Participants will then be informed of their randomization group that was determined earlier (before their baseline assessment) using the block and simple randomization techniques.

Collected data for the morphology of the residual limb, phantom phenomena, TAPES-R, PEmbS-LLA, physical function assessments, and muscle activities of the first session are baseline data and will be used for comparison to the results of the same measurements of the second session. After the first session, participants in the exercise group will be enrolled in the targeted phantom limb exercise program in addition to continuing with their usual and customary post-amputation care while participants of the control group will continue with their usual and customary post-amputation care. Participants in the exercise group will be trained on the targeted phantom limb exercise program and will have specific training sessions for three weeks at participants' homes via Zoom (<https://zoom.us/>). The researcher will make Zoom video calls to supervise participants and get assurance that all instructions are followed. After three weeks, participants of both groups will attend the test center for the second testing session. For both testing sessions, the same researcher captures the shape of the residual limb, surveys the phantom phenomena, TAPES-R, and PEmbS-LLA, assesses physical function, and conducts EMG investigations.

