#### ***Data analysis and statistics***

Different levels of comparisons will be done to explore the impact of the targeted phantom motor execution program on phantom phenomena and physical function of people with TTA. Before starting analyses, the normality of distribution of the quantitative variables will be assessed by the Shapiro-Wilk test. Since there are two groups of participants, whether participants are matched on their demographic and clinical characteristics will be explored using independent t-test and chi-square statistics. Based on our expectation of normality of distribution for the quantitative variables, if it is the case, parametric statistical tests will be used. An independent t-test will be used to compare quantitative variables within-subjects for the amputated and non-amputated sides. Similarly, Mann-Whitney test and Chi square test will be used respectively to compare ordinal and nominal categorical variables within-subjects for the amputated and non-amputated sides. An independent t-test will be analyzed to compare quantitative variables between the two groups. Similarly, Mann-Whitney test and Chi square test will be used respectively to compare ordinal and nominal categorical variables between the two groups.

Two-way analysis of variance can be used to compare the simultaneous effect of groups assignment and prosthesis embodiment on PLC. Similarly, Friedman's two-way analysis of variance will be used to compare the simultaneous effect of group assignment and surgical closure on PLC.

Spearman's correlation coefficients will be calculated to explore the potential relationship of phantom phenomena responses with participants' characteristics (i.e. age, weight, height, body mass index, length of the residual limb, the circumference of the residual limb, time after amputation, and years of prosthesis use). Moreover, the potential relationship of the phantom phenomena responses with participants' gender, type of surgery, and footedness will be explored by point-biserial correlation assessment. The potential

relationship of the phantom phenomena responses with participants' prosthesis type will be explored by partial eta square correlation assessment.

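### Surgical closure is not randomised, yet its effect on PLC is to be tested beside randomised group with no covariates, by a Friedman test that could not take them

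*Combined protocol and SAP*

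**What the plan says.** The Experimental setup section states that "the researcher will randomly assign participants to the control or exercise groups", and the Experimental protocol section says the allocation was "determined earlier (before their baseline assessment) using the block and simple randomization techniques". Neither mentions closure as something assigned or stratified on. Closure is learned later: once baseline testing is finished, the researcher contacts a third party "to get information with respect to what surgical closure technique was performed for the participant".

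The Data analysis and statistics section then plans a Friedman test to "compare the simultaneous effect of group assignment and surgical closure on PLC". Group and closure are the only factors named.

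The same section lists participant characteristics to be related to phantom phenomena by Spearman correlation: "age, weight, height, body mass index, length of the residual limb, the circumference of the residual limb, time after amputation, and years of prosthesis use". Type of surgery gets a point-biserial correlation. The baseline comparability check is between the study groups: "Since there are two groups of participants, whether participants are matched on their demographic and clinical characteristics will be explored". The last paragraph adds a logistic regression of phantom phenomena on clinical and demographic characteristics, group and physical function. It also sets a 0.05 threshold for every analysis, with effect sizes and confidence intervals reported alongside.

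**The concern.** Randomisation makes the exercise and control groups comparable in expectation. It does nothing for closure types. People with different closures may have been amputated at different times or ages, and either could be related to PLC. A test containing only group and closure assigns any such difference to closure.

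The plan has the data to reduce this problem but does not use them here. Age and time after amputation enter only one-at-a-time correlations, which adjust nothing. No comparison of closure types on baseline characteristics is planned, so an imbalance could go unseen.

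At stake is the interpretation of one secondary result: a difference that belongs to patient history could be reported, at the same threshold and under the same word as the randomised comparison, as an effect of surgical technique.

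**Working it through.** **Is closure protected by the design?** No. The Experimental setup section randomises exercise versus control only, and closure was fixed before the trial. Stratifying on closure, had it been planned, would balance closure across groups but would not make closure itself randomised.

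**Can the named test do the job?** No. Friedman's test ranks outcomes within blocks, each of which is observed under every condition. Here each participant has one group and one closure type, so both factors are between subjects. The test cannot fit the two together, and it has no place for covariates. Replacing it with an ordinary two-way analysis of variance would correct the first fault and leave the confounding.

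**How large could the distortion be?** The available text states no sample size, SD, closure distribution or correlation, so there is no figure to reproduce. What follows is illustration under assumptions:

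- Total N of 30, 40 or 60, with two closure types split equally.
- PLC treated as a continuous score with within-closure SD 1.
- Mean time after amputation differs between closure types by δ SD, with δ from 0 to 1.0.
- Within-closure correlation ρ between time after amputation and PLC of 0.3 to 0.5.
- No true closure effect; two-sided 0.05 (the plan does not state sidedness).
- A linear model stands in for the named Friedman test.

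Spurious closure difference = ρ × δ:

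- 0.3 × 0.5 = 0.15 SD
- 0.4 × 0.8 = 0.32 SD
- 0.5 × 1.0 = 0.50 SD

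With N/2 per closure type, the noncentrality of the closure test is ρδ × √N / 2. At 0.50 SD this is 0.50 × √30 / 2 = 1.37 for N = 30 and 0.50 × √60 / 2 = 1.94 for N = 60. The noncentral t distribution with N − 3 degrees of freedom then gives rejection rates of 26% and 48%.

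Simulated rejection rates for closure, model with group and closure only (3,000 replicates per cell):

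| Spurious difference | N = 30 | N = 40 | N = 60 |
|---|---|---|---|
| 0.15 SD | 7% | 8% | 9% |
| 0.32 SD | 13% | 17% | 22% |
| 0.50 SD | 25% | 33% | 49% |

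A second simulation (4,000 replicates, group-by-closure term included) gave 8% to 35% at N = 40 and 9% to 48% at N = 60 over ρδ of 0.15 to 0.50. With δ = 0 it gave about 5% at N = 20, 40 and 60. With time after amputation in the model, both simulations gave about 4% to 6% throughout. That recovery is built in: time after amputation was the only confounder simulated. Age was not simulated.

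**The case against.** **The word *effect* need not be causal.** It is ordinary analysis-of-variance vocabulary, and the plan uses it for regression predictors in general, including demographic ones. The section opens by saying the aim is to explore the impact of the exercise programme. This stands in part: a reader might infer that the trial intends to guide surgical technique, and no available section says so. It remains true that the sentence puts closure on the same footing as randomised group and does not label it exploratory or associational.

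**The question may be effect modification.** The sentence can be read as asking whether response to exercise differs by closure type. Group contrasts within a closure type are protected by randomisation, and a descriptive subgroup question does not need closure types to be comparable. That stands, and the fix allows for it. Attributing a difference in response to closure itself would still be open to confounding by age or time after amputation.

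**An adjusted model is already planned.** The logistic regression might take closure in as a clinical characteristic. That would be partial mitigation. But the text names neither closure as a predictor nor PLC as the outcome, does not present the model as the adjusted form of this comparison, and leaves the two-factor test as it is.

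**The size is all assumption.** This stands. Nothing in the documents shows that closure types differ in age or time after amputation. With no imbalance there is no inflation; at the low end it is 7-9% against 5%; 25-49% needs imbalance and correlation both at the top of their assumed ranges. PLC is not defined in the available text, nor is it said whether follow-up or change is analysed; for three-week change the assumed correlation may not apply. Pages were also removed before review and may hold a sample size or eligibility limits.

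**Conclusion.** The point holds as a matter of structure, at low to moderate severity. Closure is a non-randomised historical attribute, its comparison on PLC has no covariate, and the named procedure cannot fit the two factors or accept one. Age or time after amputation could therefore appear as a closure effect, by an unknown amount.

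Three stronger readings are not supported:

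- **That the closure result will be seriously wrong.** The documents give no imbalance, correlation or sample size, so the false-positive range is only illustrative, and it starts at the nominal 5%.
- **That the trial's main comparison is compromised.** Group is randomised, and the randomised comparison is not touched by this problem.
- **That adjustment makes closure causal.** The return to about 5% relies on a single, measured confounder. Other differences between closure types would remain.

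**What to change.** Replace the Friedman test with one regression of PLC, linear or ordinal according to its scale, containing group, closure, age and time after amputation, with the two covariates named in advance. Add the group-by-closure term if effect modification is the question, and say so. State whether the outcome is the follow-up score or the change.

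Tabulate age and time after amputation by closure type, so that a reader can see whether they differ. Report the closure coefficient with its confidence interval as an exploratory adjusted association that may still be confounded by unmeasured factors. Reserve *effect* for randomised group.

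The cost is SAP wording and two degrees of freedom for the covariates, plus one more for the interaction if it is wanted and there are two closure types. No new data are needed, since both covariates are already collected.

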### ***Experimental protocol***

At the beginning of the baseline testing session, the researcher measures participants' weight and height using a scale and stadiometer; the body mass index will be calculated using REDCap programmed formula. Then the researcher will survey prosthetic embodiment by asking participants to fill out the revised version of the Trinity Amputation and Prosthesis Experience Scales (TAPES-R) and Prosthesis Embodiment Scale for Lower Limb Amputees (PEmbS-LLA), which are brief self-administered questionnaires to assess the adjustment and interaction of people with amputation to their prosthesis. Then, the researcher will ask participants to sit on a chair within parallel bars and remove their prosthesis. The researcher will examine the residual limb and places paper skin markers on specific landmarks over their residual limb (i.e. middle of the patella, tibial tuberosity, the distal end of the residual limb). Then, participants will stand securely inside parallel bars while the researcher captures the shape of their residual limb using a 3D scanner (OMEGA Scanner 3D, Willow Wood, Ohio, USA). The morphologic characteristics of the residual limb (i.e. length, circumference, and volume) will be recorded. If the participant finds it difficult to stand without the prosthesis, the scan will be performed in sitting and note in the assessment. The participant will then return to the sitting position and placement for the electromyography (EMG) electrodes (Trigno, Delsys Inc., Massachusetts, USA) will be determined on both the intact and amputated limbs based on the standard electrode placement guideline. However, for the amputated side, since the length of the muscles has changed, the location of the EMG electrodes needs to be determined specifically for each participant based on the new muscle bulk and optimal electrical signal activity. Electromyography of the tibialis anterior, medial and lateral heads of the gastrocnemius muscle will be recorded for both sides. Electrode locations will be marked and photographed to ensure consistency with subsequent testing session recordings. The skin will be cleaned using an alcohol pad and electrodes will be attached using paper tape.

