The linear regression analysis will be used to predict the effect of predictors / independent variables (i.e. clinical and demographic characteristics, and participants group) on outcomes / dependant variables (i.e. participants' physical function variables). Logistic regression analysis will be used to predict model of phantom phenomena based on participants' clinical and demographic characteristics, participants' group and physical function measures. Prior to regression analysis, regression assumptions including the normality, linearity, homoscedasticity (i.e. having equal variances in residuals of the predictors), and absence of multicollinearity (i.e. strong linear correlation between predictors as indicated by the average of the variance inflation factor (VIF) greater than 1) will be checked. For all statistical analyses, a p-value less than 0.05 will be considered statistically significant. The effect size and confidence intervals will be reported alongside other results to provide better judgment for the potential effects. All data will be analyzed offline using IBM SPSS software (Version 22.0, IBM Corp, New York, USA).

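### If the listed characteristics are carried into the regressions, weight, height and BMI, and probably the two duration variables, would be highly collinear, and the planned VIF check does not deal with it

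*Combined protocol and SAP*

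**What the plan says.** Under Experimental protocol, weight and height are measured at the visit and "the body mass index will be calculated using REDCap programmed formula".

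Under Data analysis and statistics, the quantitative characteristics are itemised once, for pairwise correlations: "Spearman's correlation coefficients will be calculated to explore the potential relationship of phantom phenomena responses with participants' characteristics", namely "age, weight, height, body mass index, length of the residual limb, the circumference of the residual limb, time after amputation, and years of prosthesis use".

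The regression paragraph of that section describes its predictors only in general terms. For the linear model on physical function they are "clinical and demographic characteristics, and participants group". For the logistic model on phantom phenomena they are "participants' clinical and demographic characteristics, participants' group and physical function measures". Multicollinearity is among the assumptions to be examined beforehand, defined as "strong linear correlation between predictors as indicated by the average of the variance inflation factor (VIF) greater than 1) will be checked". The paragraph gives no predictor list, no selection rule and no action if the check fails.

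**The concern.** BMI is a function of two other variables on the list, so once weight and height are in a model it adds almost nothing. Years of prosthesis use is, for most people, time after amputation less the delay to fitting. Five of the eight listed characteristics therefore hold about three pieces of information.

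An analyst looking for the regression predictors has only this list to go on for quantitative characteristics, and nothing tells them to leave any out. If all of it goes in, the model tries to separate effects that the data can hardly separate. A real association with body size or with time since amputation could be spread over two or three unstable coefficients and missed at the 0.05 level. The redundant terms also use up degrees of freedom. The regressions exist to show which characteristics predict function and phantom phenomena, so this affects part of what they are meant to deliver.

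**Working it through.** **Inputs from the plan.** There are eight quantitative characteristics, BMI is calculated by formula from weight and height, and the multicollinearity criterion is an average VIF above 1. The plan states no VIF to reproduce. The text available for this review gives no distributions for these variables and no sample size, so all of those are assumptions here.

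**Formula.** For predictor j, VIF = 1/(1 − R²), where R² comes from regressing predictor j on the other predictors. This is also the j-th diagonal element of the inverse correlation matrix. The standard error of the coefficient grows by √VIF.

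**Body size.** BMI = weight/height². Assumed: height mean 172 cm, SD 7 to 10; weight mean 82 kg, SD 12 to 20; weight-height correlation r from 0 to 0.5. Large-sample simulation gives:

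| Weight SD | Height SD | r | VIF weight | VIF height | VIF BMI | Weight and height only |
|---|---|---|---|---|---|---|
| 12 | 7 | 0.3 | 160 | 50 | 156 | 1.10 |
| 15 | 9 | 0.5 | 120 | 40 | 91 | 1.33 |
| 18 | 10 | 0.5 | 97 | 28 | 73 | 1.33 |
| 20 | 10 | 0.3 | 80 | 20 | 76 | 1.10 |
| 15 | 9 | 0 | 65 | 22 | 86 | 1.00 |

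Over the whole assumed range the VIFs are about 15 to 65 for height, 54 to 196 for weight and 68 to 155 for BMI. At the ends of a rounded range of 15 to 195, standard errors grow by √15 = 3.9 to √195 = 14.0. The VIFs stay finite because BMI is a nonlinear function of weight and height.

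**Duration pair.** Years of use = time after amputation − lag to fitting. For two variables, VIF = 1/(1 − r²), which gives 5.3 at r = 0.90, 10.3 at r = 0.95 and 50.3 at r = 0.99.
- Mean time 3 to 12 years and mean lag 0.5 to 2 years: r is about 0.93 to 0.999 and VIF about 7 to 986.
- Median time 5 years with log SD 0.5, and an exponential lag with SD 2 years: r is about 0.90 and VIF about 5.
- Median time 5 years with log SD 0.9 and lag SD 0.25 years: VIF over 1,000.

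**Whole model.** This takes all eight characteristics plus group, with weight SD 15, height SD 9, r = 0.4, mean time about 8 years and mean lag 1 year. The reduced set is age, BMI, limb length, circumference, time after amputation and group. Entries are medians over simulated samples.

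| Assumed N | Average VIF, all nine | Group VIF, all nine | Average VIF, reduced set | Largest VIF, reduced set |
|---|---|---|---|---|
| 20 | 120 | 1.68 | 1.38 | 1.66 |
| 40 | 77 | 1.24 | 1.15 | 1.25 |
| 100 | 61 | 1.08 | 1.05 | 1.09 |

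At N = 30 the group VIF is about 1.4 with all nine predictors and about 1.2 with the reduced set, so its standard error differs by a factor of √(1.4/1.2) = 1.08.

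**The plan's criterion.** Since R² ≥ 0, every VIF is at least 1, and the average equals 1 only if all sample correlations are exactly zero. Six independently generated predictors gave an average above 1 in every simulated sample. The criterion therefore flags the harmless set (average 1.05 to 1.38) and the redundant one (61 to 120) alike.

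**The case against.** The strongest reply is that the list belongs to the Spearman correlations, which take one characteristic at a time, so collinearity does not arise there. The regression paragraph never says that weight, height and BMI, or both durations, enter one model. This stands: the link is an inference. It is a natural one, because no other quantitative list is offered, but a reader who concludes that the plan's condition fails by construction goes further than the text.

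A second reply is that the plan already checks for multicollinearity, and VIFs of this size would be seen. That stands only in part. The check would trip, but it trips for practically any set of predictors, and no consequence is attached to it.

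Third, the duration result depends on the data. The plan does not say how long fitting takes, whether use is interrupted or how years of use are counted. With a VIF near 5 the pair would pass a cut-off of 10, so failure under any cut-off cannot be claimed for it.

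Fourth, the Spearman analyses are exploratory, and reporting related characteristics side by side is ordinary description. This stands. The only caution there is that overlapping measures should not be counted as separate findings when "a p-value less than 0.05 will be considered statistically significant" is applied to each.

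**Conclusion.** The concern holds conditionally. If the itemised characteristics are carried into the regressions, the body-size trio has VIFs of roughly 15 to 195 across the assumed distributions. The duration pair is probably highly collinear too, at about 5 to over 1,000 according to the assumed lag. The separate coefficients of these five variables would be very imprecise, and the plan's own check would not guide the analyst to a remedy.

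A reader might infer that the models cannot be fitted, that their coefficients cannot be interpreted at all, or that the estimated effect of group is compromised. The documents do not support this. The dependence of BMI on weight and height is not exactly linear, so the models can be fitted. In the simulations above, the VIFs of age, limb length and circumference stay at about 1.1 to 1.8, and that of group at about 1.1 to 1.7. The damage is confined to the redundant covariates and the degrees of freedom they use. It deserves correction because the change is almost free, not because the randomised comparison is at risk.

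**What to change.** In the regression paragraph, list the predictors of each model. Enter either BMI alone, or weight and height without BMI, but never all three. Enter only one of time after amputation and years of prosthesis use. Replace the average-VIF criterion of 1 with a workable threshold for each predictor and state what will be done when it is exceeded. Without that change the literal condition would still fail after the redundant terms are removed (average 1.05 to 1.38).

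This changes analysis wording only; data collection stays the same. It is not entirely free of loss:
- BMI alone gives up separate height information. With weight 85 kg (SD 18), height 1.72 m (SD 0.10) and r from 0.2 to 0.5, BMI shares only about 0.3% to 11% of its variance with height. Keeping weight and height instead avoids this loss at a VIF of 1/(1 − 0.2²) = 1.04 to 1/(1 − 0.5²) = 1.33, for one more degree of freedom.
- Dropping one duration variable gives up any separate effect of fitting delay.

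The Spearman table can stay as planned, read as descriptive, with overlapping measures not counted as independent associations.

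### The logistic model for phantom phenomena is unpenalised with no limit on predictors; if the listed characteristics enter together (about 14 to 17 slopes), it separates in small samples and overstates the group effect in moderate ones

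*Combined protocol and SAP*

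**What the plan says.** All of this is in the Data analysis and statistics section of the combined protocol and SAP.

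- **Logistic model.** It is to "predict model of phantom phenomena based on participants' clinical and demographic characteristics, participants' group and physical function measures".
- **Linear models.** The predictors are "clinical and demographic characteristics, and participants group"; the outcomes are "participants' physical function variables". Physical function is therefore a predictor only in the logistic model.
- **Characteristics.** The regression paragraph does not itemise them. The nearest list belongs to the correlation analyses of phantom phenomena. Its quantitative items are "age, weight, height, body mass index, length of the residual limb, the circumference of the residual limb, time after amputation", plus years of prosthesis use, which makes eight. Gender, type of surgery and footedness are handled by point-biserial correlation, so as binary. Prosthesis type is handled separately, and its number of categories is not given.
- **Safeguard.** Multicollinearity is to be checked before regression and is defined as an average variance inflation factor above 1. No action is stated if the check fails.
- **Reporting.** For every analysis "a p-value less than 0.05 will be considered statistically significant", with effect sizes and confidence intervals alongside.

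The Experimental setup section describes a "2-arm, parallel, open label, non-blinded randomized controlled trial" with "an in-person baseline visit and an in-person follow up visit at WinPO". The sample size does not appear in the text supplied for review. It may stand in pages that were removed, so its absence is not held against the plan.

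**The concern.** Maximum likelihood logistic regression needs enough responses in the smaller outcome category for each slope it estimates. With too few, some combination of predictors often sorts the responses perfectly (separation). Odds ratios then have no finite estimate, and what the software prints for them and their confidence intervals is meaningless. With somewhat more data the fit converges, but the log odds ratios are biased away from zero. Both problems bear directly on the effect sizes and intervals that the section promises.

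The characteristics also overlap by construction. The Experimental protocol section has body mass index calculated by formula from measured weight and height, and all three are on the list. In the linear models, unneeded covariates cost residual degrees of freedom and raise R-squared by chance.

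**Working it through.** The plan states no figure that can be reproduced here. The inputs are the slope count, taken from the documents, and assumed values for N, response prevalence and the group odds ratio.

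**Slope count**

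- Linear models: 8 quantitative + 3 binary + 1 or 2 for prosthesis type + 1 for group = 13 to 14.
- Logistic model: the same, plus 1 to 3 physical function measures (phantom motor execution, FSST, possibly plantar load) = 14 to 17.

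**Separation, by formula.** With a 50:50 outcome unrelated to k predictors in general position, the chance of complete separation is P(Bin(N−1, 0.5) ≤ k), from Cover's counting theorem.

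| N | k = 14 | k = 16 |
|---|---|---|
| 20 | 0.99 | 1.00 |
| 30 | 0.50 | 0.77 |
| 40 | 0.05 | 0.17 |
| 50 | 0.002 | 0.01 |

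**Separation and bias, by simulation.** There were 400 trials per cell, with k = 14 or 16, prevalence 50% or 70%, a true group odds ratio of 2 (log odds ratio 0.693) and all other slopes null. Weight, height and body mass index were entered together. Separation was detected by linear programming and the remaining trials were fitted by maximum likelihood. Ranges run over the four combinations of k and prevalence. The last column is the mean estimated group log odds ratio divided by its true value, among trials that did not separate.

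| N | Separated | Mean ratio to truth |
|---|---|---|
| 20 | 99–100% | too few fits |
| 30 | 55–90% | unstable, few fits |
| 40 | 10–45% | 2.3–3.1 |
| 50 | 2–13% | 1.7–2.1 |
| 60 | 0.3–3% | 1.5–1.8 |
| 80 | under 1% | 1.3–1.5 |
| 100 | under 1% | 1.2–1.3 |
| 150 | 0% | 1.1–1.2 |
| 200 | 0% | 1.03–1.09 |

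Averaging the four cells gives (1.46 + 1.75 + 1.57 + 1.69)/4 = 1.62 at N = 60 and (1.26 + 1.23 + 1.28 + 1.33)/4 = 1.28 at N = 100. On the odds-ratio scale, a true 2 becomes about 2^1.6 = 3.0 and 2^1.25 = 2.4.

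Means are pulled up by extreme fits. The medians at N = 60 run from 0.90 to 1.13, or 1.30 to 1.63 times 0.693. At N = 100 they run from 0.83 to 0.88, or 1.20 to 1.27 times. A separate simulation with a true odds ratio of 2.5 and 16 slopes gave median estimates of 3.8 at N = 60 and 3.1 at N = 100. The log ratios are ln 3.8/ln 2.5 = 1.46 and ln 3.1/ln 2.5 = 1.23. A repeat gave about 3.7 and 2.9, or 1.43 and 1.16.

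**Events per slope.** This is N × (smaller proportion)/k. At N = 100 it is 100 × 0.5/14 = 3.6 at best and 100 × 0.3/16 = 1.9 with a 70:30 split. Ten per slope would need 10 × 14/0.5 = 280 to 10 × 16/0.3 = 534 participants.

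**Linear models, 13 slopes, covariates not prognostic.** Relative confidence-interval width for group, against the unadjusted comparison, is [t(0.975, N−14)/t(0.975, N−2)] × √[(N−3)/(N−15)]. At N = 20 this is (2.447/2.101) × √(17/5) = 2.15. If w is that relative width, covariates break even when they explain 1 − 1/w² of outcome variance. Expected R-squared with no true association is 13/(N−1).

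| N | Relative width | Break-even variance explained | Chance R-squared |
|---|---|---|---|
| 20 | 2.15 | 78% | 0.68 |
| 30 | 1.39 | 48% | 0.45 |
| 40 | 1.24 | about 35% | 0.33 |
| 60 | 1.13 | 22% | 0.22 |
| 100 | 1.07 | 13% | 0.13 |

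**Collinearity check.** A variance inflation factor is 1 only for a predictor uncorrelated with all the others in the sample. The average therefore exceeds 1 for practically any real predictor set, so the check cannot tell a mild overlap from a severe one.

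**The case against.** The strongest reply is that the regression paragraph names categories of predictors and does not say that every listed characteristic enters at once. The 12-item list belongs to the correlation analyses, and the regression text never refers to it. That stands: the slope count is conditional on this reading. It does not remove the point. If a smaller set is meant, the plan does not name it or say how it is chosen, and the same correction is needed.

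A reader might also infer more than the documents support:

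- **That the models fail at any plausible single-centre size.** N is unavailable, separation is rare above about N = 50, and the bias fades to 3 to 9% by N = 200.
- **That all the regressions carry the physical function measures.** In the linear models these are the outcomes.
- **That the linear models necessarily lose precision.** At N = 60 to 100 the interval is only 7 to 13% wider with 13 slopes, and covariates explaining 13 to 22% of outcome variance would offset that.
- **That the trial's group comparison depends on these models.** The same section plans direct between-group tests (t-test, Mann-Whitney, chi-square).

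Finally, the plan does check collinearity, the one device that bears on overlapping predictors. As specified, it flags almost any predictor set and triggers nothing.

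**Conclusion.** The concern holds for the logistic model, conditional on the listed characteristics being entered together. Over an assumed N of 20 to 100, the model usually separates at about 30 or below and sometimes at 40. At 60 to 100 it overstates the group log odds ratio by roughly 60% falling to 25%. These sizes rest on 14 to 16 slopes, prevalence of 50 or 70%, a true odds ratio of 2 and no other true effects. The linear models are a secondary matter: the loss is serious only at N of about 20 to 30, and only if the covariates explain little of the outcome. The documents do not support a claim of failure in every regression or at every size. The change should be made, but the direct group comparisons do not depend on it.

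**What to change.** **Logistic model**

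- Name in advance a short predictor list that includes group.
- Limit total slopes in relation to the expected number in the smaller response category, and state the ratio used.
- Do not enter body mass index together with both weight and height.
- Fit by Firth's penalised likelihood. SPSS 22 is the only software named, so confirm that it can do this or add software that can.
- Label the model exploratory.

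**Linear models**

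- Name in advance a short covariate list scaled to the sample size.
- If associations of the remaining characteristics with physical function are wanted, add them as exploratory single-variable analyses. The planned correlations cover phantom phenomena only, so these associations would otherwise be lost.

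**Cost.** SAP wording, and possibly a software add-on. Mutually adjusted coefficients for every characteristic would no longer be reported.
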